### **3.3 Study Design**

#### **3.3.1 Basic PRODUCE Study Design:**

This study will employ a series of individual N-of-1 trials that compare the SCD to a modified SCD using a collaborative approach between patients, parents, and their clinical team. Patients will enter the study on a usual (non-SCD) diet and will have a minimum 1-week run in period for diet planning and baseline data collection before beginning their assigned treatment. Treatment periods will be assigned in blocks of two (e.g., AB) with the goal of each patient completing two balanced treatment blocks (e.g., ABAB) where treatment 'A' represents SCD and treatment 'B' represents modified SCD. Patients will be randomized to either the SCD or modified SCD as their starting intervention and alternate between these two conditions for four 8-week treatment periods. The study design is summarized in Figure 1.

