### **3.5.4 Early Withdrawal of Participants**

If a patient experiences symptom flare, leading to either the diet intervention being stopped, medication being changed, or the need for surgical intervention, their participation in the N-of-1 protocol will be discontinued. In addition, patients who become pregnant during the study will be automatically withdrawn, as will patients that have  $\geq 7.5\%$  nonintentional weight loss. Patients may also withdraw if they feel that they are unable or unwilling to continue the assigned diet or data collection. Participants will be dropped from the study if they have a symptom tracking response rate of  $<50\%$  in the baseline period that does not improve after reasonable attempts by research coordinators (as outlined in the study SOPs) to assist participants in improving data collection. Because completion of stool fecal calprotectin is required to advance from one treatment period to another, a participant who never collects and sends in a stool specimen will be dropped at that point in the study. All data from such participants will be retained and analyzed. Patients who wish to terminate a treatment period early (and switch to the next assigned treatment) will not be considered withdrawals. Participants who wish to end their study participation early, but have completed at least two full diet treatment periods (i.e., A1 and B1), will have the option to discontinue participation and terminate the protocol early. Participants who choose to discontinue from the study in these instances will schedule a time to come into clinic to

receive their final study results and complete the end of survey questionnaire regarding their N-of-1 experience. These participants will not be considered withdrawals.

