### **3.6.2 Statistical Methods**

An overview of the statistical analysis can be found below. A formal data and statistical analysis plan will be prepared as a separate document

*Analysis of Individual N-of-1 Trials:* For the first treatment period only, there will be a 1-week run-in period as the participant gradually transitions from their usual diet to the intervention diet. A gradual transition is not needed beyond the first treatment period. For the first period, we will discard the first 7 days of data including the first weekly measurement. Based on clinical experience we expect that diet effects on symptoms wash out by 1 week. Thus, for all subsequent treatment periods we will discard the first 7 days of data including the first weekly measure during each treatment period. At the end of each person's N-of-1 trial, statistical analysis will be performed to compare results on the two treatments. Each N-of-1 trial requires a separate analysis which is automated to run in the background once each trial is completed. The analysis consists of running Bayesian models that compare the average response on each of the two treatments and baseline diet. Models will incorporate the appropriate scales for the outcomes (e.g. normal distributions for continuous variables, multinomial distributions for categorical variables) and the appropriate representation of the function linking the expected outcome to the predictors (e.g., cumulative logit link for ordinal outcomes).

Results will be reported for all study measures (stool frequency, stool consistency, PROMIS Pain interference, PROMIS GI Symptoms, fecal calprotectin) to enable patients to weigh symptoms that are most important to them. For each outcome, each patient will be provided with an estimate

## USING SINGLE SUBJECT (N-OF-1) DESIGNS TO ANSWER PATIENT-IDENTIFIED RESEARCH QUESTIONS – AIM 1

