of the (1) difference in efficacy between the two diets; and (2) probability that each treatment is better than the other; as well as the (3) difference in efficacy between each diet and the baseline level; and (4) probability that each treatment is better than the baseline. Results will be portrayed numerically and graphically. We will develop educational materials to aid patients and clinicians in interpretation (Appendix B). Posterior probabilities of outcomes will be calculated using an interface that incorporates open-source R software interfacing through Rjags with open-source JAGS software. The R code creates the Bayesian model, loads the stored data and chooses intelligent starting values that are then fed into JAGS to return the Markov chain Monte Carlo (MCMC) simulations of the joint posterior distribution. The R package will accept input from the Eureka platform to construct models and return results back to Eureka for display.

Statistical analyses will be completed and patients will be given results of their individual N-of-1 studies if they complete at least one paired treatment period and there is enough data in both treatment periods to perform valid statistical analysis.

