**Meta-Analysis of N-of-1 Trials:** The collection of individual N-of-1 trials can be thought of as a set of studies whose results can be combined as in a meta-analysis. The data can be considered as a multilevel structure in which a set of patients is studied with each patient having a set of measurements. Standard multilevel mixed model methods will be used to estimate the average effect and variance within and across patients. Across patient values estimate the average effect in the population of patients studied, while the within-patient estimates describe an improved estimate of each patient's true effect assuming exchangeability across patients. We will fit these models using a Bayesian multilevel model with non-informative priors in order to obtain posterior distributions of the within and between effect sizes. We will then compare the multilevel patient estimates with those from the patient's data alone in order to determine how much the effects change and how much additional precision these estimates gain. We will also include between-patient covariates to account for variability and to test for heterogeneity of treatment effects (HTE). We hypothesize that HTE may exist based on age, sex, disease (CD or UC/IC), disease activity (mild or moderate), maintenance medication use, disease location, and disease type (inflammatory or penetrating). The model will include the baseline levels of the outcomes which will enable estimates of the effect of the study diets relative to the unrestricted diet. We will also fit models that adjust for trends over time and account for correlation and carryover. Analyses will use the appropriate probability distribution and link function for the outcome variable type (e.g. normal distributions for continuous outcomes and ordinal logistic regression with a cumulative logit link for scales).

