## **Appendix E: Patient Handout Instructions for Stool Collection**

**See Separate Document**

**Appendix F: 3-day Diet Recall Questions**  
**See Attached**

## Appendix G: N-of-1 Trial Results Display

iii. Text with each gauge

- c. Chance that SCD is Better than your Usual Diet
  - a. Text: You have a [X]% chance that you showed improvement in your stool frequency and a [X]% chance your stool frequency got worse.
  - d. Chance that the Modified SCD is Better than your Usual Diet
    - a. Text: You have a [X]% chance that you showed improvement in your stool frequency and a [X]% chance your stool frequency got worse.
2. Chance that the SCD is Better than the Modified SCD
  - a. Text: There is a [X]% chance that your stool frequency was better on the SCD and a [X]% chance that it was better on the Modified SCD.

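### The individual diet comparison has no stated time term, so change over time can enter a child's result with a sign set by the starting diet; after one pair, diet and period order are the same thing

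*Combined protocol and SAP*

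**What the plan says.** Section 3.3.1 randomises only the starting diet. Patients then "alternate between these two conditions for four 8-week treatment periods", giving ABAB or BABA.

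Section 3.5.4 lets patients stop early. Those who "have completed at least two full diet treatment periods (i.e., A1 and B1), will have the option to discontinue participation" are not counted as withdrawals, and they return to clinic to "receive their final study results and complete the end of survey questionnaire". Section 3.6.2 agrees: individual results are given "if they complete at least one paired treatment period and there is enough data in both treatment periods" for a valid analysis. What counts as enough or valid is not defined.

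On the individual model, section 3.6.2 says: "The analysis consists of running Bayesian models that compare the average response on each of the two treatments and baseline diet". The missing-data paragraph of the same section describes this analysis as having no covariate adjustment. For each outcome the patient is told the "probability that each treatment is better than the other". Appendix G words this for stool frequency as "There is a [X]% chance that your stool frequency was better on the SCD", with the complementary figure for the modified SCD.

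Time is addressed only under the meta-analysis: "We will also fit models that adjust for trends over time and account for correlation and carryover".

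**The concern.** Within one patient, the second-assigned diet is always the later one. If symptoms change for any reason other than the diet contrast, an unadjusted comparison of averages credits or debits that change to whichever diet came later. Two children with the same course and no diet difference could receive opposite answers because of their starting draw.

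The documents give reasons to expect some change over time:

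- Entry requires a raised inflammatory marker on the usual diet (3.5.1), so some regression to the mean is plausible, at least for those markers.
- Improvement on the SCD is said to take about 1 month for symptoms and 2 months for inflammation (3.3.1), or 2 to 3 months (3.1.1). It can therefore run beyond an 8-week first period.
- The two diets share most of their content (3.3.3), and only the first-assigned diet directly follows the usual diet.
- Section 3.3.1 itself says it is uncertain whether sequence matters.

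The stake is the individual answer, which section 3.6.1 names as the primary goal of Aim 1 and ties to the choice of diet. The pooled estimate is largely protected by the 1:1 allocation of starting diet and by the planned trend models.

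**Working it through.** **Plan's own figure.** There is none for the individual analysis. The 90% power in section 3.6.1 concerns the pooled comparison, and this point does not depend on it.

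**Inputs from the documents.** Four 8-week periods in alternation; the first 7 days and first weekly score of each period discarded (3.6.2), leaving weeks 2 to 8, or 7 weekly scores per period; one fecal calprotectin value per treatment period (Table 1).

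**Inputs assumed.** Within-patient weekly residual SD s = 5 T-score points (range 4 to 7), independent residuals, flat prior, no true diet difference, improvement of b points per 8 weeks.

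**Step 1: time offset.**
- One pair: mean weeks 5 and 13, a difference of 8.
- ABAB: mean weeks (5+21)/2 = 13 and (13+29)/2 = 21, again a difference of 8.

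A linear drift of b per 8 weeks therefore appears as a diet difference of b in both cases, favouring the later diet. BABA reverses which diet that is.

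**Step 2: can time be separated from diet?**
- As period effects: one pair has three coefficients (mean, diet, period) and a design of rank 2, so it cannot be done.
- Calprotectin after one pair: two on-diet values, so diet and time are one contrast.
- Weekly scores with a linear trend: the squared correlation of diet with week is 0.80 for one pair and 0.19 for ABAB. Variance inflation is 1/(1−0.80) = 5.0 and 1/(1−0.19) = 1.24; the standard error grows by √5.0 = 2.2 and √1.24 = 1.11.

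**Step 3: what the report would show.** The unmodelled drift also inflates the estimated residual SD. The within-diet variance of week number is 4 for one pair and 4 + 64 = 68 for ABAB. So SD* = √(s² + v(b/8)²) with v = 4 or 68, SE = SD* × √(4/n) with n = 14 or 28, and the probability for the later diet is about Φ(b/SE).

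| b per 8 weeks | One pair, s = 5 | ABAB, s = 5 |
|---|---|---|
| 1 | SE 2.68, 65% | SE 1.93, 70% |
| 2 | SE 2.69, 77% | SE 2.04, 84% |
| 3 | SE 2.70, 87% | SE 2.22, 91% |

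For s from 4 to 7, b = 2 gives 82% to 70% (one pair) and 88% to 77% (ABAB); b = 3 gives 92% to 79% and 94% to 85%. With the starting diet reversed, the same figures attach to the other diet.

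**Step 4: early transient instead of linear drift.** Suppose only period 1 differs, by 3 points. The unadjusted bias is 3 after one pair and 3/2 = 1.5 after ABAB. Exponential settling (assumed total gain 10 points, time constant 4 to 8 weeks) gives 2.8 to 3.5 after one pair and 1.4 to 2.0 after ABAB. In the period-1 case a linear time term reduces the ABAB bias from 1.5 to 0.8. It leaves the one-pair bias at 3, because a step between two periods is exactly the diet contrast.

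**The case against.** **The size is assumed.** This stands. The documents give no drift rate. Three points per period is the minimally important difference of section 3.6.1 repeated every 8 weeks, or 9 points from period 1 to period 4. At 1 point the report shows only 65% or 70%. Selection is on inflammatory markers, not on pain interference; recent medication changes are excluded (3.5.2), and a flare leading to a medication change ends participation (3.5.4). Residual correlation matters too: at a weekly correlation of 0.5 properly allowed for in the standard error (4.05 and 2.82 at SD 5), 2 points give about 69% and 76%.

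**The text is incomplete.** Section 3.6.2 calls itself an overview and promises a separate formal plan; the remark on covariates sits in a missing-data paragraph; Appendix G is available only in part; and interpretation materials are planned. So the claim is that no time term is stated, not that one is ruled out. The data condition does not help: more observations in the same two periods do not remove order.

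**Stronger readings that the documents do not support.**
- A reader might infer that every one-pair result is fully confounded with time. That is exact for period order and for calprotectin. Weekly scores can separate a linear trend, at five times the variance.
- A reader might infer that stopping early is the whole problem and four periods cure it. Under linear drift the ABAB bias is the same.
- A reader might instead infer that the second block never helps. Under an early transient it roughly halves the bias.
- A reader might infer that the between-diet gauge must be withheld from early stoppers. The protocol chose to give these patients a result, and a clear statement beside it addresses the harm.

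**Conclusion.** The point holds for the individual results. As written, the plan compares averages by diet with no stated time term, in a design where the second-assigned diet is always 8 weeks later on average. Change over time therefore biases the individual diet difference, in a direction set by the starting diet. This is bias, so the argument in section 3.6.1 that false-positive control is unnecessary does not answer it.

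The 8-week offset and the variance factors of 5.0 and 1.24 follow from the design and the discard rule. The probabilities in the table are illustrations that rest on the assumed drift, SD and independence, and they refer to a weekly T-score, not to stool frequency. The bias is the same for one pair and four periods only if drift is linear; for an early transient, one-pair patients are hit about twice as hard. The population estimate is not at issue.

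**What to change.** 1. In section 3.6.2, include a linear time term in the individual model for patients with all four periods. Note there that it only partly removes a non-linear early change.
2. For patients with one pair, present the diet-versus-diet result in Appendix G with an explicit statement that, with one period of each diet, a diet effect cannot be separated from change over time.
3. Supply these patients with their trend-adjusted estimate from the multilevel model already planned in section 3.6.2, when it is available.

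Withholding the one-pair gauge altogether is optional.

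The cost is a small change to the R/JAGS template and to the report wording, and individual standard errors about 11% wider for four-period patients (variance ×1.24). No diet, visit or data collection changes.

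### The main pooled model, as described, has no treatment-period level and no serial correlation, so for the repeated symptom outcomes it overstates how much patients differ in their response to diet

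*Combined protocol and SAP*

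**What the plan says.** Section 3.3.1 has each patient "alternate between these two conditions for four 8-week treatment periods", so the unit to which diet is assigned is the period, with two periods per diet in a complete trial.

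Section 3.6.2, under Meta-Analysis of N-of-1 Trials, gives the pooled data two levels: "a set of patients is studied with each patient having a set of measurements". The variance components match: "Standard multilevel mixed model methods will be used to estimate the average effect and variance within and across patients". Patient-specific diet effects enter through partial pooling, which is to give a better estimate of each patient's "true effect assuming exchangeability across patients". The plan will report posteriors for the within- and between-patient effect sizes, and will compare the pooled patient estimates with those from each patient's own data.

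Serial dependence appears once: "We will also fit models that adjust for trends over time and account for correlation and carryover". No structure is given, and these models come in addition to the main one. No period effect or between-period variance is named there or in the sample-size text of 3.6.1. Section 3.6.2 calls itself an overview and adds: "A formal data and statistical analysis plan will be prepared as a separate document". That document is not among those supplied.

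On data retained per period, "we will discard the first 7 days of data including the first weekly measure during each treatment period", which leaves 7 of 8 weekly scores.

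**The concern.** A patient's diet contrast is the mean of two SCD periods minus the mean of two modified-SCD periods. Two things besides a personal response to diet move it: week-to-week correlation, which makes period means noisier than independent residuals imply, and any disturbance shared by a whole period. A model with only patients and independent measurements has no term for either. It expects a small error in the contrast, sees a larger spread across patients, and assigns most of the excess to the patient-by-diet variance.

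That variance is a stated product of the pooled analysis, and it sets the shrinkage of every patient estimate. If it is inflated, the trial reports more between-patient difference in response than exists, and the pooled patient estimates keep noise as if it were personal response. The repeated periods in ABAB are what allow a reproducible response to be told from one bad period, and the two-level model does not use that information.

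**Working it through.** **The plan's own figure.** The documents give no heterogeneity SD to reproduce. The nearest figure is the power claim in 3.6.1: 90% for 3 points with up to 60 patients, except when σ_t = 5 and ρ > 0.5. Neither σ_t nor the within-patient SD is defined. Read σ_t as the between-patient SD of the diet effect and take residual SD 10, 8 weekly scores per period and AR(1) over the whole trial. Then SE² = (σ_t² + 100·c'Rc)/60, where c is the diet contrast and R the correlation matrix. At σ_t = 5 and ρ = 0.5, c'Rc = 0.266, so SE² = (25 + 26.6)/60 = 0.861, SE = 0.928, and power = Φ(3/0.928 − 1.96) = 89.9%. For ρ of 0.6 to 0.8 it is 86.6% to 87.9%. At σ_t of 3 or 4 it is at least 91.7%. The stated pattern is attainable, and nothing here shows it to be wrong.

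**Inputs for the check.** From the documents: four periods, two per diet, 7 retained weekly scores each, up to 60 patients. Assumed: residual SD 6, ρ = 0.3, period SD s of 0 to 3 T-score points, true heterogeneity 0.

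**Step 1, variance of a period mean.** With AR(1) inside a period it is (36/7)·k + s², where k = 1 + 2·Σ(1 − j/7)·0.3^j for j = 1 to 6, which is 1.682. So it is 8.65 + s².

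**Step 2, variance of a patient's diet contrast.** Four period means, each with weight ±1/2, give 4 × (1/4) × (8.65 + s²) = 8.65 + s². A period variance therefore enters in full.

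**Step 3, what the two-level model expects.** It estimates residual variance from the scatter of the 14 scores on each diet: r = (14/13)·[36 + s² − (8.65 + s²)/2]. It then expects contrast error r·(1/14 + 1/14) = r/7.

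**Step 4, what it calls heterogeneity.** Spurious variance = (8.65 + s²) − r/7. The weight given to the patient's own contrast is this divided by 8.65 + s². The correct weight is 0.

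| Period SD s | Contrast variance | r/7 | Spurious variance | Spurious SD | Weight |
|---|---|---|---|---|---|
| 0 | 8.65 | 4.87 | 3.78 | 1.9 | 0.44 |
| 1.5 | 10.90 | 5.05 | 5.86 | 2.4 | 0.54 |
| 2 | 12.65 | 5.18 | 7.47 | 2.7 | 0.59 |
| 3 | 17.65 | 5.57 | 12.09 | 3.5 | 0.68 |

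Letting the correlation also run across period boundaries changes the SDs only to 1.89, 2.38, 2.70 and 3.45.

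**Step 5, how far a serial term helps.** These are REML fits standing in for the Bayesian model, with true heterogeneity 0.

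- Whole-period shifts, residual SD 5, ρ = 0.3, 300 simulated trials, period SD 0, 2, 3 and 5. With AR(1) added to the two-level model, the median spurious SD is 0.00, 1.63, 2.52 and 4.31. With a patient-by-period effect as well, it is 0.00, 0.00, 0.00 and 0.12.
- Smooth drift (AR(1) 0.9 per week, SD 3 or 5, plus white noise; 30 trials): AR(1) alone gives 0.0 to 0.2.
- Disturbances not aligned with periods (illnesses of 1 to 3 weeks, flares of 4 to 8 weeks, blocks of 10 to 16 weeks; residual SD 6, 40 trials each): AR(1) alone gives 0.02 to 0.03. The plain two-level model gives 2.1 to 2.3.

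**Step 6, real heterogeneity.** With true SD 3 and period SD 3, residual SD 6, the estimates are 4.6 (two-level), 3.9 (with AR(1)) and 2.8 (with a period level). If serial correlation is confined to within periods and the noise drifts slowly, a true SD of 3 can be estimated at only 0.9 to 2.5. The serial term should therefore cross period boundaries.

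**Step 7, what is not harmed.** For the average diet effect, type I error was 7–8% with AR(1) and 6–7% with the period effect (z-tests, 300 trials). A diet-by-covariate test had 6% type I error in both the two-level and the AR(1) models at period SD 3 (200 trials). The inflated slope variance also widens these standard errors.

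**The case against.** The strongest reply is that 3.6.2 is an overview. Describing the data as multilevel is not a model equation, accounting for correlation could include a patient-by-period effect, and the separate analysis plan may contain one. All of that is possible, so this is not evidence that the final analysis will omit the level. But the protocol does not require the term, and it leaves correlation to additional models.

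A reader might infer that a serial-correlation term does not cure the problem at all. The checks do not support that. No between-period variance is stated anywhere. An intercurrent illness need not last a period or begin at a diet switch, and school terms do not line up with staggered enrollment. For such disturbances AR(1) removes nearly all of the inflation in the SD. The residual problem needs whole-period shifts. Adherence is a plausible source, although adherence that differs by diet is arguably part of that patient's diet effect.

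A reader might also infer that the trial will falsely declare effect modification, or that the average comparison is invalid. The plan tests heterogeneity through patient covariates, and neither those tests nor the average effect is materially disturbed (Step 7). The separate individual reports are outside this point.

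Two limits on the remedy also stand. Fecal calprotectin has one value per period, so a period effect cannot be separated from residual error. Patients who stop after A1 and B1 are retained, but they add nothing that separates period variance from patient-by-diet variance.

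**Conclusion.** The concern holds for the reported between-patient SD of the diet effect and for the shrinkage of patient estimates, in outcomes measured repeatedly within a period. With the main model as written, a spurious SD of about 1.9 points arises from modest serial correlation alone. It rises to 2.4, 2.7 and 3.5 at period SDs of 1.5, 2 and 3, against the 3-point minimally important difference in 3.6.1. A serial term is sufficient for smooth or non-aligned disturbance and only partly effective for whole-period shifts (about 2.5 left at period SD 3).

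The sizes rest on assumed residual SD, correlation and period SD, none of which the documents give, and they scale with those values. The simulations used REML on a weekly score. The same logic applies to daily outcomes, which were not simulated.

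**What to change.** In 3.6.2, and in the separate analysis plan, specify for daily and weekly outcomes that the primary pooled model has:

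- a random patient-by-diet effect;
- a random period-within-patient effect;
- residual serial correlation over calendar time across periods, not only inside them.

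Report the heterogeneity SD and the shrunken patient estimates from that model, and keep the two-level model as a sensitivity analysis. Exempt fecal calprotectin. State that separating period from patient-by-diet variance relies on patients with at least one repeated diet period.

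The cost is a period variance term and a serial-correlation structure in the pooled Bayesian model, plus a short paragraph of text. No new data are needed. The downside is small: less apparent heterogeneity, stronger shrinkage and wider uncertainty for the heterogeneity SD. Where no period shift existed, the period term did no visible harm: false declaration of heterogeneity by a variance test was 2.0%, against 3.7% with AR(1) alone.
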